15.2.2 Compensation for Participation

The compensation for participation amounts are provided in [Table 11](#).

Table 11: Compensation for Study Subjects

Visit(s)	Amount Per Visit (\$)*
Screening	25-
Each Randomized Subject	200-
Total Compensation	225-

*Compensation will be given in the form of gift cards.

15.2.3 Medical Care for Research-Related Injury

All non-exempt research involving human subjects shall, at a minimum, meet the requirement of 32 CFR 219.116(a)(6).

If a subject is injured because of participation in this research and is a DoD healthcare beneficiary (eg, active duty in the military, military spouse or dependent), the subject is entitled to medical care for that injury within the DoD healthcare system, as long as the subject remains a DoD healthcare beneficiary. This care includes, but is not limited to, free medical care at Army hospitals or clinics.

If a subject is injured because of participation in this research and is not a DoD healthcare beneficiary, the subject entitled to medical care for that injury at an Army hospital or clinic; medical care charges for care at an Army hospital or clinic will be waived. The subject is also entitled to care for that injury, but such care for that injury at other DoD (non-Army) hospitals or clinics may be limited by time, and the subject's insurance may be billed. It cannot be determined in advance which Army or DoD hospital or clinic will provide care. If the subject obtains care for research-related injuries outside of an Army or DoD hospital or clinic, the subject or the subject's insurance will be responsible for medical expenses.

15.3 Written Informed Consent

The informed consent process and document will be reviewed and approved by US Investigational Review Board, USAMRMC ORP and Sponsor's representative prior to initiation of the study. The consent document contains a full explanation of the possible risks, advantages, and alternate treatment options, and availability of treatment in the case of injury, in accordance with the United States Code of Federal Regulation, Title 21, Part 50 (21 CFR 50). The consent document indicates that by signature, the subject permits witnessing of applicable study procedures by the sponsor's representative, as well as access to relevant medical records by the sponsor's representative and by representatives of the FDA. The sponsor's representative will submit a copy of the initial IRB and sponsor's representative-approved consent form to the FDA

and will maintain copies of revised consent documents that have been reviewed and approved by US Investigational Review Board and ORP.

A written informed consent document, in compliance with 21 CFR Part 50, 32 CFR Part 219, and the Belmont Principles and HIPAA Authorization will be signed by the subject before any study-related procedures are initiated for that subject. This consent document must be retained by the investigator as part of the study records. Each subject will receive a copy of the signed informed consent document. The investigators or their designees will present the protocol in lay terms to individual subjects. Questions on the purpose of the protocol, protocol procedures, and risks to the subjects will then be solicited. Any question that cannot be answered will be referred to the PI. No subject should grant consent until questions have been answered to his/her satisfaction. The subject should understand that the study product is an investigational drug and is not licensed by the FDA for commercial use, but is permitted to be used in this clinical research. Informed consent includes the principle that it is critical the subject be informed about the principal potential risks and benefits. This information will allow the subject to make a personal risk versus benefit decision and understand the following:

- Participation is entirely voluntary,
- Subjects may withdraw from participation at any time,
- Refusal to participate involves no penalty, and
- The individual is free to ask any questions that will allow him/her to understand the nature of the protocol.
- A description of this clinical trial will be available on <http://www.ClinicalTrials.gov>, as required by US law.

Should the protocol be modified, the subject consent document must be revised to reflect the changes to the protocol. If a previously enrolled subject is directly affected by the change, the subject will receive a copy of the revised informed consent document. The approved revision will be read, signed, and dated by the subject.

16 Data Handling and Recordkeeping

The primary source document for this study will be the subject's medical record. If separate research records are maintained by the investigator, the medical record and the research records will be considered the source documents for the purposes of auditing the study. The source documents will be retained at the site.

For this study, an EDC database system will be used for the collection of the study data in an electronic format. The EDC database system will be designed based on the protocol requirements, the approved eCRF layouts and specifications, and in accordance with 21 CFR Part 11. The eCRF layouts and specifications define and identify the applicable source data that will be collected and captured into the EDC database system. The applicable source data will be electronically transcribed by the site designee onto the eCRF (data entry screens) in the EDC database system. The investigator is ultimately responsible for the accuracy of the data transcribed on the eCRF. Data monitoring will be performed in the EDC database system by the study monitor and the designated Data Management group.

A detailed data management plan will be written and approved by the study team and the Principal Investigator prior to study start, with approval by the sponsor's data manager in the USAMMDA CSSD. All updates to the data management plan must be approved before study close-out and database lock.

16.1 Inspection of Records

The sponsor's representative or designee will be allowed to conduct site visits at the investigation facility for the purpose of monitoring any aspect of the study. The investigator agrees to allow the monitor to inspect the drug storage area, investigational product stocks, drug accountability records, subject charts, study source documents, and other records relative to study conduct.

Subjects' health information is used to report results of research to the sponsor's representative and Federal regulators and may be reviewed during study audits for compliance with study plans, regulations, and research policies. The informed consent document indicates that by signature, the subject permits access to relevant medical records by the sponsor and its representatives, U.S. Investigational Review Board and by representatives of the FDA in order to audit or monitor the study data.

Upon a subject's termination from the trial, completed eCRFs will be ready and available for on-site review by the sponsor's representative or the designated representative within 14 days after receipt of the subject's data.

16.2 Retention of Records

The Principal Investigator must maintain all documentation relating to the study for a period of 2 years after the last marketing application approval, or if not approved for 2 years following the discontinuance of the investigational product for investigation. If it becomes necessary for the sponsor's representative or designee or the FDA to review any documentation relating to the study, the investigator must permit access to such records.

Completed, monitored eCRFs will be stored in a secure location by the sponsor's representative or designee. A copy of each completed eCRF will be retained by the investigator.

The Principal Investigator will be responsible for retaining sufficient information about each subject, ie, name, address, telephone number, driver's license number and subject identifier in the study, so that the sponsor's representative, the IRB of record, the FDA, employees of USAMRMC, or other regulatory authorities may have access to this information should the need arise.

It is the policy of the USAMRMC that data sheets are to be completed for all subjects participating in research (Form 60-R, Volunteer Registry Data Sheet). The data sheets will be entered into this Command's Volunteer Registry Database. The information to be entered into this confidential data base includes the subject's name, address, and Social Security Number; study title; and dates of participation. The intent of this data base is twofold: first, to readily answer questions concerning an individual's participation in research sponsored by USAMRMC; and second, to ensure that USAMRMC can exercise its obligation to ensure research subjects are adequately warned (duty to warn) of risks and to provide new information as it becomes available. The information will be stored at USAMRMC for a minimum of 75 years. The Volunteer Registry Database is a separate entity and is not linked to the study database.

17 Publication Policy

All data collected during this study will be used to support this IND. All data may be published in the open medical or military literature with the identity of the subjects protected. Anyone desiring to publish or present data obtained during the conduct of the study will conform to Salus Research policies and then forward the publication for review to the Commander, USAMMDA or designee and [contact] prior to submission.

18 List of References

Appendix D. ePRO Electronic Diary Information

Each subject will record the start and stop times for chewing gum on the ePRO Electronic Diary Information System. This data will be collected via the internet. The subject will receive three emails per day containing a link to the respective ePRO form. Each form will be identified by "Day" and "Time of Chew". For example, for Day 1, the forms will be identified as: Day 1 – Chew 1 (morning), Day 1 – Chew 2 (afternoon), Day 1 Chew 3 (evening). Over the course of the study there will be a total of 12 forms (one for each chew) to be completed.

The subject will open the email and click the link to the ePRO form. On the form, the subject will enter the start and stop times for each chew and "submit" this information in real time.

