5.5.3 Rationale for Four Day Proof of Concept Study

The primary objectives for the Phase 1/2a study were to evaluate the safety and tolerance to the active gum. In the Phase 2a study, the proof of concept efficacy assessment for plaque accumulation and changes of gingivitis conditions were included and the assessments occurred on Days 0 (baseline), 14, 28 and 34 (follow-up). The rationale for conducting a 4-day treatment study is to determine if the active gum (vs. placebo gum) can reduce plaque regrowth during early time points (4 days).

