5.6.1.2 Systemic Reactions

Based on review of the nonclinical data, no direct systemic AEs from administration of the study drug are expected. Review of the clinical data indicates that subjects participating in this study may experience: abdominal discomfort and flatulence. Subjects will be asked at each visit to report any new symptoms or concomitant medications used.

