7.1 Study Measurements (Endpoints)

The primary endpoint is:

- Incidence of AEs including change from baseline in vital signs

The secondary endpoints are:

- Change from baseline in QHT (Day 4 QHT minus baseline QHT)
- QHT based on sub-scores from designated regions of the mouth (upper jaw, lower jaw, buccal and lingual surface)

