- The first chew will be administered under supervision in the clinic. The subject will be instructed to chew one tablet of gum for 20 minutes. Chewing should be balanced as equally as possible between both sides of the mouth.
- After chewing the gum for the designated time, the subject will be given a used product bag to store the chewed gum. The evaluator will inform the subject to label this bag with the time and date of the chew.
- After the chewing gum is stored in the used product bag, the subject will complete the start and stop times for chewing gum on the electronic diary information system (ePRO). The subject will enter this information while in the clinic.
- The study drug will be dispensed for unsupervised use. The subject will receive:
 - 13 gum tablets for their unsupervised use along with 13 individual used product collection bags.
 - Subjects will be given instructions for chewing the gum.
 - a. The gum will be chewed for 20 minutes preferably after a meal or every 4 to 6 hours (3 times a day). Chewing will be balanced as equally as possible between both sides of the mouth for a maximum of 3 chews per day.
 - b. After completing each 20 minute chew, subjects will store the used gum in the used product collection bags provided to them.
 - c. Subjects will label each used product collection bag with the date and time of chew. (A separate bag will be used for each chew).
 - d. After each chew, subjects will record the start and stop time of the chew on the electronic diary information system - ePRO (Instructions provided in [Appendix D](#))
 - e. Subjects will be informed that they must bring all of the used product collection bags back to the clinic for Visit 3
- Subjects will be told that no oral hygiene procedures of any kind (teeth brushing, flossing or mouth wash rinse) will be allowed while on study treatment (Day 0, 1, 2, 3 and 4).
- AEs from first chew will be collected.
- Concomitant medication will be recorded.

9.1.3 Unsupervised Treatment, Study Days 0, 1, 2, and 3

After the first supervised chew is completed, the subjects will be released from the clinic. There will be a total of 11 unsupervised, self-administered chews. The subjects will chew one tablet of the gum (study drug) for 20 minutes every 4 to 6 hours, preferably after a meal, for a maximum of 3 chews per day according to the schedule in [Table 6](#).

Table 6: Schedule for Unsupervised Chews:

Time ^a	Day 0	Day 1	Day 2	Day 3
After Breakfast ^b	N/A	1	1	1

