11.2.2 Solicited Adverse Event

This section is not applicable.

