11.4 Recording Adverse Events

11.4.1 Methods/Timing for Assessing, Recording and Analyzing Safety Measurements (Endpoints)

AEs and SAEs will be assessed at each study visit and documented in the source records. All AEs will be recorded on the eCRFs using accepted medical terms and/or the diagnoses that accurately characterizes the event. SAEs will be documented using the SAE paper form. It should be noted that the form for collection of SAE information is not the same as the AE eCRF.

Where the same data are collected on both forms, the forms must be completed in a consistent manner. For example, the same event term should be used on both forms.

When a diagnosis is known, the AE term recorded on the eCRF will be the diagnosis rather than a constellation of symptoms. The investigator will assess and record for all AEs/SAEs: a description of the event (if the event consists of a cluster of signs and symptoms, a diagnosis should be recorded rather than each sign and symptom); onset date and time, and resolution date and time; intensity (recorded as mild, moderate or severe); relationship to study drug (recorded as unrelated, unlikely related, possibly related, probably related and definitely related); outcome (recorded as recovered, recovering, resolved with sequelae, not resolved, fatal, ongoing (end of study) or unknown if applicable); action taken with the study product (recorded as no action taken, dose reduced, interrupted, discontinued). When an event has not resolved by study closure, it will be documented on the AE eCRF as “ongoing”.

The timeframe for the collection of AEs and SAEs for each subject begins at the first administration of investigational product (Visit 2 - Day 0) through Visit 3 - Day 4.

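### Transient symptoms over the 11 unsupervised chews are captured by one open question at Day 4, although the diary form opened at every chew asks only for times

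*Protocol*

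**What the plan says.** - **Endpoint.** Protocol 7.1 gives the primary endpoint as "Incidence of AEs including change from baseline in vital signs". Safety and tolerability form one primary objective (6.1), and no separate tolerability measure is defined.
- **Solicited events.** Protocol 11.2.2 reads "This section is not applicable".
- **When AEs are asked about.** Protocol 11.4.1: "AEs and SAEs will be assessed at each study visit and documented in the source records". The Day 0 list in 9.1.2 limits this to the supervised dose ("AEs from first chew will be collected"). The next AE assessment is on Day 4 (9.1.4). The AE row of Table 4 is marked on Day 0 and Day 4 only.
- **How they are asked.** Protocol 5.6.1.2: "Subjects will be asked at each visit to report any new symptoms or concomitant medications used". SAP listing LREF15 holds a yes/no AE question by visit. Neither document describes an itemised symptom list.
- **What must be recorded.** Protocol 11.4.1 requires onset and resolution date and time for each AE. Protocol 11.3 requires the causality judgement to weigh when the event began relative to dosing.
- **Window.** The collection period "begins at the first administration of investigational product (Visit 2 - Day 0) through Visit 3 - Day 4". After that, 11.4.2 requires serious AEs to be followed to resolution and related ones to be reported whenever they become known.
- **Diary.** Appendix D describes three emailed links a day and one form per chew, 12 in all. On content it says "Each subject will record the start and stop times for chewing gum on the ePRO Electronic Diary Information System". No symptom item is described.

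**The concern.** Some of the reactions that the protocol lists as risks (5.6.1.1 and 5.6.1.2) are sensations: altered or lost taste, throat tightness, abdominal discomfort, flatulence. If such an event has passed by the Day 4 morning, no examiner can find it. It enters the primary endpoint only if the subject remembers it and thinks it worth mentioning.

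Dating has the same problem. The diary timestamps each chew, but the start and end of any symptom during unsupervised dosing are reconstructed from memory up to about four days later. The time-to-dose comparison that 11.3 asks for therefore has one side recorded near the event and the other recalled.

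At stake are the completeness and dating of mild tolerability events in a trial with 13 subjects per arm, where a few reports make up most of the AE table.

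**Working it through.** **1. The plan's own counts.** Three chews a day for 4 days gives 3 × 4 = 12 forms, as Appendix D states. Table 6 gives 2 + 3 + 3 + 3 = 11 unsupervised chews, and the supervised one makes 12. So 11/12 = 92% of doses have no scheduled AE enquiry until Day 4.

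**2. Which events are exposed to the gap.** Of the eight reaction types judged related in phase 2a (Protocol 5.5.2):
- Three are visible and fall within the Day 4 oral examination if still present: coated tongue, tongue pigmentation, tooth discoloration.
- Five are felt by the subject: abdominal discomfort, flatulence, dysgeusia, throat tightness, ageusia.

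The gap concerns the second group, and any visible sign that clears before Day 4.

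**3. Scale of the AE table.** Inputs: 54 AEs and 64 subjects over 28 days (5.5.2); 26 subjects here (5.7).
- Earlier rate: 54 / (64 × 4 weeks) = 0.21 AEs per subject-week. This credits all 64 with full exposure; 58 completed per protocol, so it is slightly low.
- Expected here: 0.211 × 26 × 4/7 = 3.1 AEs in both arms together, or 0.211 × 26 × 5/7 = 3.9 if five days are counted.

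This is an order of magnitude only. The earlier study enrolled a gingivitis population, used doses up to 75 mg, and its count covers all AEs, not just felt ones. It does show that one or two missed reports would be visible in the summary.

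**4. Illustration of lost capture.** Let p be the true proportion of subjects with at least one transient felt event, and c the share of those subjects who report it at Day 4. Neither is in the documents, so both are assumptions. With 13 independent subjects in an arm:

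P(at least one recorded) = 1 − (1 − p·c)^13

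| p | c = 1 | c = 0.75 | c = 0.5 |
|---|---|---|---|
| 5% | 48.7% | 39.2% | 28.0% |
| 10% | 74.6% | 63.7% | 48.7% |
| 20% | 94.5% | 87.9% | 74.6% |

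For p = 20%: 1 − 0.80^13 = 94.5% with full capture, and 1 − 0.90^13 = 74.6% with half.

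**5. Effect on the arm comparison.** If both arms lose the same share, recorded incidence is c·p in each. The ratio is unchanged, (c·p₁)/(c·p₀) = p₁/p₀. The absolute difference becomes c·(p₁ − p₀).

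**6. Recurrence.** Incidence proportion counts subjects with at least one AE (Protocol 12.1.1.1). If a symptom recurs three times and each occurrence is recalled independently with probability 0.5, then 1 − 0.5³ = 87.5% of affected subjects are still counted. With p = 20% the detection chance is then 1 − (1 − 0.20 × 0.875)^13 = 1 − 0.825^13 = 91.8%. The 50% column is therefore pessimistic for recurring symptoms. The event rate per subject-week, which counts events, gets no such protection.

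**The case against.** The best defence is that an open question at each visit is an ordinary way to collect AEs, that declining solicited AEs is an explicit choice, and that the recall period is at most about four days. Subjects also have emergency and non-emergency contacts on the vial label (Protocol 7.3.2, Figure 1), and Section 11 says safety is monitored throughout. All of this stands. No passages contradict each other, and the method is not an error.

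A reader might infer four stronger things, which the documents do not support:

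- *That the primary endpoint as a whole rests on unprompted recall.* Subjects are asked about new symptoms at each visit (5.6.1.2), and LREF15 records the answer to an AE question. Vital signs are measured on Day 0 and Day 4 (11.1.1), soft and hard tissues are examined at both visits, and new or worsened soft-tissue findings become AEs (11.1.3.1). A symptom-oriented physical examination follows on Day 4.
- *That taste and throat symptoms are the expected signal at 30 mg.* Protocol 5.5.2 reports dysgeusia only at 50 and 75 mg, and throat tightness and ageusia only at 75 mg. Among the felt related reactions, only abdominal discomfort and flatulence appear for the 4–30 mg groups, each once across those groups. Section 5.6.1.1 still lists the others as risks for these subjects. No durations are given, so that any of them is brief is an inference.
- *That the AE window is shorter than the earlier study's.* The Day 14, 28 and 34 schedule in 5.5.3 refers to plaque and gingivitis assessments. It does not show how long AEs were collected, and that study dosed for 28 days.
- *That the arm comparison is biased.* Equal under-reporting leaves the ratio intact, and the AE comparison is a descriptive side-by-side display (12.1).

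What survives is that none of these safeguards reaches a felt symptom that has resolved and been forgotten by Day 4, or supplies a time for one that is remembered.

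**Conclusion.** The point holds in a limited form. For transient, subject-felt events during the 11 unsupervised chews, capture and timing depend on one open question at Day 4, while a form completed at each chew collects no symptom information. This is a cheap improvement to the primary endpoint's data, not a flaw that invalidates it.

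The size of the loss cannot be derived from the documents. The fall from 94.5% to 74.6% assumes that 20% of subjects are affected, that half of them report it, and that subjects are independent. It is smaller if recall is better or symptoms recur. The dating problem does not depend on those assumptions: onset and resolution times are required, and for unsupervised chews nothing planned records them near the event.

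The documents give no adequate ground for extending AE collection beyond Day 4, so none is recommended here.

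**What to change.** 1. **Diary (Appendix D).** Add one item to each existing form: *Any symptom since your previous form? Yes/No; if yes, describe and give the start and end time.* Keep it open and identical in both arms. Symptoms after the final Day 3 form would still be picked up only at Day 4.
2. **Day 4 interview (9.1.4 and 11.4.1).** Use the subject's diary entries to cue the AE questions, by the same script in both arms, and take onset and resolution times from the entries where available. State who reads the entries and when.
3. **SAP (LREF16 and Section 7.1.1).** Flag each AE first reported through the diary, so that AEs obtained without that prompt can be tabulated separately and remain comparable with the earlier study.

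The cost is one diary item, a short interview script, one flag variable, and reconciliation of diary entries with the AE page. The known downside is more mild AEs recorded in both arms, which the flag makes visible. Doses, visits, randomisation and plaque procedures are unaffected.

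The diary change must be in place before the first subject is dosed. If data collection is already complete (the protocol estimated August 2016 and the final SAP is dated February 2017), the remaining step is to state in the study report how AEs were elicited between the first chew and Day 4.
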